Twice daily administration of exenatide has been tested in a pilot trial on PD patients with encouraging results.^{51,52} This single-blind trial on 45 patients showed that those taking the drug for 12 months improved to a significant degree on the Movement Disorders Society's Unified Parkinson's Disease Rating scale (MDS-UPDRS, +2.7 points) compared to a decline (-2.2 points) in control patients not administered the drug. It also showed a highly significant improvement in the Mattis dementia rating scale (MDRS, +2.8 points) in patients on exenatide compared to a decline (-3.5 points) in control patients. A follow-up study a year after the trial ended (i.e., a year off exenatide) found preservation of both the motor and cognitive benefits of the trial.⁵² These results suggest a disease modifying effect of the GLP-1 receptor agonist, providing evidence that the pathogenesis of PD can be slowed or stopped. These findings are being pursued in a placebo-controlled, once weekly exenatide (Bydureon) trial on PD cases in London (<https://foxtrialfinder.michaeljfox.org/trial/3583/>; <http://www.ucl.ac.uk/exenatide-pd>).

Once daily liraglutide, however, may prove superior to once weekly exenatide in treating PD. While both these GLP-1 receptor agonists can reduce systemic insulin resistance by causing weight loss, once daily liraglutide may be more potent in that regard because it has recently been found more effective than once weekly exenatide in reducing body weight.⁵³ Liraglutide, which is currently indicated for once-daily administration in adults with T2D up to 1.8 mg/day and for weight management at 3.0 mg/day, is also more effective than exenatide (twice daily or weekly) in reducing hyperglycemia,⁵³⁻⁵⁵ which has diverse detrimental effects on neuronal function.⁵⁶⁻⁵⁸ Unlike the case for exenatide, there is direct evidence from ex vivo insulin stimulation studies that liraglutide applied directly to brain tissue can reduce insulin resistance there in mild cognitive impairment (MCI) cases in a mouse model of AD.⁴³ Finally, liraglutide exerts neuroprotective effects in the mouse MPTP model of PD at 25 nmoles/kg body weight, but exenatide does not.⁵⁹

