The final determination of protocol violations, and therefore the composition of the PP population, will be made prior to unblinding the database and will be documented separately. Analysis of all efficacy

Table 1 (from Aviles-Olmos et al., 2013⁵¹)

Changes in the score on LED, dyskinesia rating scale, Mattis DRS-2, MADRS, and PDQ39 summary index between baseline and month 14

	Baseline	6 months	12 months	Difference, baseline to 12 months	14 months	Difference, baseline to 14 months
	Mean (SD)	Mean (SD)	Mean (SD)	Mean (SD); 95% CI	Mean (SD)	Mean (SD); 95% CI
LED						
Exenatide	973 (454)	1011 (518)	997 (446)	24.3 (123.6); -37, 78	1015 (467)	42.3 (137); -22, 107
Conventional PD medication	977 (493)	1061 (613)	1121 (620)	143.7 (223.6); 49, 238	1125 (638)	148.0 (232); 50, 246
Dyskinesia rating scale, on medication						
Exenatide	2.3 (2.8)	2.5 (4.1)	3.3 (4.5)	1.0 (4.2); -1.0, 3.0	3.2 (4.0)	1.0 (3.8); -0.8, 2.7
Conventional PD medication	2.6 (2.9)	3.5 (3.9)	2.5 (2.7)	-0.04 (2.7); -1.2, 1.1	2.7 (3.5)	0.1 (4.3); -1.7, 1.9
MATTIS DRS-2						
Exenatide	140.1 (7.7)	142.4 (2.3)	142.3 (2.5)	2.2 (6.4); -0.8, 5.2	142.9 (2.0)	2.8 (6.0); -0.1, 5.6
Conventional PD medication	139.5 (4.5)	138.2 (5.1)	136.6 (6.1)	-2.8 (5.3); -0.6, -5.0	135.9 (8.5)	-3.5 (5.8); -1.1, -6.0
MADRS						
Exenatide	10.9 (5.1)	8.6 (4.2)	9.0 (4.5)	-1.9 (4.6); -4.1, 0.3	10.2 (6.7)	-0.7 (5.9); -3.5, 2.1
Conventional PD medication	11.0 (5.4)	11.3 (6.5)	11.4 (5.6)	0.5 (4.5); -1.4, 2.4	12.4 (5.6)	1.5 (4.7); -0.5, 3.4
PDQ39 summary index						
Exenatide	19.2 (13.5)	18.1 (13.4)	19.6 (13.0)	0.4 (11.4); -4.9, 5.7	21.5 (19.6)	2.3 (11.6); -3.1, 7.7
Conventional PD medication	24.5 (12.8)	25.2 (15.8)	24.0 (15.3)	-0.6 (11.2); -5.3, 4.2	23.4 (16.0)	-1.2 (9.1); -5.0, 2.7

variables will be performed on the FAS and PP population. The FAS population will serve as the primary population for the analysis of efficacy data. Analyses based on the PP population will be considered as a sensitivity analysis. Subjects will be analyzed for efficacy according to the treatment to which they were randomized.

All safety outcomes will be analyzed using the Safety population. Subjects will be analyzed for safety according to the treatment they actually received.

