Descriptive statistics: The study population will be described using demographic, baseline, and subject characteristics. Descriptive statistics of demographic, baseline, and subject characteristics will be based on the Safety population. A detailed description of subject disposition will include:

- A summary of data on subject discontinuations including reason for withdrawal
- A summary of protocol violations and deviations

All screened subjects will be accounted for in the disposition summaries. The number and percentage of subjects included in each analysis population will be summarized.

Baseline and subject characteristics will include a summary of the following:

- Subject demographics
- Medical history including family history

- Physical examination findings
- Prior and concomitant medications/therapies
- HoMA-IR and QUICKI index at baseline
- MDRS-2 scores at baseline
- MDS-UPDRS scores at baseline
- Non-Motor Symptoms Scale (NMSS) scores at baseline
- PDQ-39 Quality of Life scale scores at baseline
- Delis-Kaplan Executive Function System (DKEFS), Geriatric Depression Scale, and Parkinson's Anxiety Scale scores at baseline

Inferential Statistics on Primary Efficacy Parameter(s): The primary analysis of efficacy endpoint (changes in UPDRS, NMSS, and MDRS-2 scores between baseline and Week 54) will be assessed using a two-sided, two-sample unequal-variance t-test to evaluate the differences in end points between the active and placebo cohorts. Multiple regression analysis will be used for comparisons of between-cohort differences in these outcomes over time. General linear models will be used to evaluate possible associations between baseline characteristics and the primary endpoints. Analysis of covariance (ANCOVA) will be used to evaluate possible effects of peripheral insulin sensitivity and treatment group (independent variables) on the primary end points (dependent variable). Hochberg's method for adjustment for multiple testing separately for the primary end points and secondary endpoints will also be used.

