The last UPDRS, NMSS, and MDRS-2 scores prior to first drug administration will be used as the baseline value in the model and to calculate change from baseline clinical scores. To calculate the change from baseline at week 54, the clinical scores at week 54 will be used. Missing values will be imputed using the last observation carried forward (LOCF) method, including clinical scores on the discontinuation visit. Baseline values will not be carried forward. This methodology will be applied to all treatment groups (liraglutide and placebo).

The assumptions of normality and homogeneity of variance will be explored using probability and residual plots. Data will be tested for normality using the Shapiro-Wilk test. If any of the assumptions are found to be violated, an appropriate transformation of the data or non-parametric test will be considered.

Sensitivity analyses of the primary efficacy endpoint will be performed on the PP population using the same methods described for the FAS population. Summaries of clinical scores, including the change from baseline, will be presented at each visit (i.e., baseline, Week 28, and Week 54). No adjustments have been made to the Type I error rate for the multiple comparisons of the primary or secondary endpoints since this is a phase II study; therefore, results should be interpreted appropriately. No statistical testing within treatment groups will be performed.

Inferential Statistics on Secondary Efficacy Parameter(s): Analyses of secondary efficacy endpoints will be conducted on the FAS and PP populations. The following secondary efficacy endpoints will be analyzed using an approach similar to that described for the primary efficacy endpoints:

- Change in PDQ-39 scores for each domain and total score between baseline and week 54.
- Change in Delis-Kaplan Executive Function System (DKEFS) between baseline and week

- Change in Geriatric Depression Scale between baseline and week 54
- Change in Parkinson's Anxiety Scale scores between baseline and week 54

The safety outcomes of this study will be the following:

- Adverse events
- Serious adverse events
- Clinical laboratory parameters
- Geriatric Depression Scale
- Vital signs
- Physical examination.
- 12-lead ECGs

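### Missing week-54 scores are handled by LOCF in the primary analysis and in its only labelled sensitivity analysis, so nothing planned tests the no-change assumption, which Table 1 makes doubtful for controls

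*Combined protocol and SAP*

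**What the plan says.** Under Inferential Statistics on Primary Efficacy Parameter(s), the primary comparison is an unequal-variance t-test on change from baseline to week 54 in UPDRS, NMSS and MDRS-2. For missing data: "Missing values will be imputed using the last observation carried forward (LOCF) method, including clinical scores on the discontinuation visit". Baseline is not carried forward, and the Full Analysis Set (FAS) requires a post-baseline efficacy score. LOCF therefore applies only to subjects who have such a score; the others are left out.

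The one analysis labelled as a sensitivity analysis is this: "Sensitivity analyses of the primary efficacy endpoint will be performed on the PP population using the same methods described for the FAS population". It changes who is analysed and keeps the missing-data rule.

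Three other planned items bear on the point:
- "A summary of data on subject discontinuations including reason for withdrawal" (Descriptive statistics)
- "Summaries of clinical scores, including the change from baseline, will be presented at each visit", that is, baseline, week 28 and week 54
- "Multiple regression analysis will be used for comparisons of between-cohort differences in these outcomes over time"

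None of them is given a different missing-data rule or presented as a check on LOCF. The documents contain no mixed model for missing data, multiple imputation, reference-based, tipping-point or completers analysis.

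**The concern.** LOCF assumes that a subject's score does not change between the last assessment and week 54. Parkinson's disease is progressive, the hypothesis concerns one-year change, and after baseline the on-treatment efficacy scales are scheduled only at weeks 28 and 54, so a carried score can be months old.

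Table 1 suggests that the assumption fits the two arms differently. The control MDRS-2 change at 12 months is minus "2.8 (5.3); -0.6, -5.0" and at 14 months minus "3.5 (5.8); -1.1, -6.0", so an early score flatters a control subject. Exenatide hardly moves after month 6. Applying one rule to both arms need not act equally on both.

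What drug stoppers do after stopping is a second unknown. The background reports that follow-up a year off exenatide "found preservation of both the motor and cognitive benefits of the trial", but those patients had completed a year on drug, and early stoppers may differ. At stake are the size of the week-54 estimate and a reader's ability to see how far it depends on an untested assumption. LOCF also counts carried scores as if they had been observed at week 54.

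**Working it through.** **Inputs.** Table 1 mean MDRS-2:

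| Arm | Baseline | 6 mo | 12 mo | 14 mo |
|---|---|---|---|---|
| Exenatide | 140.1 | 142.4 | 142.3 | 142.9 |
| Control | 139.5 | 138.2 | 136.6 | 135.9 |

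Changes at 6 months are +2.3 and −1.3 (differences of means). Changes at 12 months are +2.2 and −2.8 as tabulated. I match 6 months to week 28 and 12 months to week 54. Losses are 2/38 drug and 4/19 placebo, from the fall from 38/19 to 36/15 in the Sample Size Calculation; equal 20% dropout is an added scenario.

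**The plan's effect.** Differences of means give (142.3 − 140.1) − (136.6 − 139.5) = 2.2 + 2.9 = 5.1, the planned difference. The tabulated changes give 2.2 − (−2.8) = 5.0, used below.

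**Time of the carried score.** The plan carries discontinuation-visit scores, so week 28 is not the only possible source. I take months 3, 6 and 9, assuming linear change between visits: drug +1.15, +2.3, +2.25; control −0.65, −1.3, −2.05.

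**LOCF estimate.** With loss fractions pD and pP and carried changes d and c:

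LOCF = [2.2 + pD(d − 2.2)] − [−2.8 + pP(c + 2.8)]

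Example, the plan's losses at month 6: [2.2 + (2/38)(0.1)] − [−2.8 + (4/19)(1.5)] = 2.205 + 2.484 = 4.69.

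**Targets.** If benefit persists off drug, the target is 5.0. If drug stoppers lose all benefit (assumption), it is 5.0(1 − pD): 4.74 at the plan's losses and 4.00 at 20%.

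| Losses | Carried from | LOCF | Error if benefit persists | Error if all is lost |
|---|---|---|---|---|
| 2/38, 4/19 | month 3 | 4.49 | −0.51 | −0.25 |
| | month 6 | 4.69 | −0.31 | −0.05 |
| | month 9 | 4.84 | −0.16 | +0.11 |
| 20%, 20% | month 3 | 4.36 | −0.64 | +0.36 |
| | month 6 | 4.72 | −0.28 | +0.72 |
| | month 9 | 4.86 | −0.14 | +0.86 |

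**Break-even.** With equal dropout, the error changes sign once stoppers lose the fraction [(c + 2.8) − (d − 2.2)]/5.0 of the benefit: 3.2/5.0 = 64% at month 3, 1.4/5.0 = 28% at month 6, 0.7/5.0 = 14% at month 9.

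**False positives.** Suppose there is no drug effect, both arms follow the control course, and the plan's losses are carried from week 28. The bias is (2/38 − 4/19) × 1.5 = −0.24. The standard error is √(6.4²/38 + 5.3²/19) = 1.60 with Welch df 42.8. The noncentral t gives a two-sided error of about 5.2%.

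**Cost of an MMRM.** Simulation at the plan's losses used normal data, SD 6.4 and 5.3 at both visits, losses at random after week 28, an assumed week-28/week-54 correlation of 0.5 to 0.7, and no baseline term. An MMRM with covariance by arm averages 5.0, with SE 1.69-1.73 and power 80-82%. LOCF averages about 4.7, with SE 1.60 and power 81-83%. The SE ratios are 1.69/1.60 = 1.06 and 1.73/1.60 = 1.08. With covariance pooled across arms, MMRM power is 77-79%.

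**The case against.** The strongest reply has four parts.

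**Table 1 is weak evidence for this trial.** Its controls received conventional medication rather than placebo, the pilot was single-blind and tested another drug, and no interval is given for the 6-to-12-month change. The 1.5-point decline is smaller than the 2.2-point half-width of the 12-month control interval, (5.0 − 0.6)/2. This stands. Table 1 supports concern; it neither disproves the assumption here nor measures the bias.

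**LOCF is conservative.** A reader might infer this from the month-6 figures, where the error at the plan's loss split stays against the drug even if all benefit is lost. The documents do not support it as a general statement. It holds for scores carried from week 28, but the plan also carries discontinuation scores. From about month 9 the error at that split becomes +0.11, and with equal dropout the sign turns at anything from 14% to 64% loss of benefit.

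**An MMRM can do worse.** If 20% of the drug arm stop and lose all benefit, an MMRM under missing-at-random gives about 5.0 against a target of 4.00, further off than LOCF's 4.72 at month 6. This stands, and is why an MMRM alone is not a sufficient remedy.

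**The other outputs would show a problem.** The disposition and visit summaries may reveal imbalance, and the regression over time could use week-28 data. None is stated to re-estimate the week-54 effect without LOCF.

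A reader might also infer that subjects who stop drug have no later efficacy assessment. The Withdrawal Criteria suggest this but do not say it, and the point does not depend on it.

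**Conclusion.** The concern holds and should be fixed. LOCF is the stated rule for FAS subjects with a post-baseline score, the only labelled sensitivity analysis reuses it, and no planned analysis varies the no-change assumption. The sponsor's own sizing data make that assumption doubtful for controls and roughly right for exenatide after month 6.

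On MDRS-2 the distortion is modest: across the scenarios shown it runs from 0.64 points too low to 0.86 too high on an effect of 5.0. The sign depends on when subjects leave, how losses split between arms, and whether stoppers keep their benefit. These figures rest on one pilot's means, linear change between visits, and dropouts following their arm's course up to the carried score. Table 1 gives no MDS-UPDRS or NMSS means by visit, so nothing comparable can be computed for those scales. A claim of serious false-positive inflation would go too far.

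**What to change.** In Inferential Statistics on Primary Efficacy Parameter(s):

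1. For each primary endpoint, replace LOCF as the main handling of missing data with an MMRM on observed week-28 and week-54 scores. Include baseline score, arm, visit, arm-by-visit and baseline-by-visit, with unstructured covariance fitted by arm, since the planned Welch test already allows unequal variances.
2. Pre-specify a reference-based analysis (missing drug-arm scores imputed from placebo) or a tipping-point analysis. It is needed because the MMRM treats drug stoppers like drug-arm continuers.
3. Keep the planned LOCF analysis as supplementary, since it uses the discontinuation-visit scores.

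At minimum, leave LOCF as primary and add item 2 beside it.

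Imputing week 54 from discontinuation scores is not a workable shortcut. Unless stoppers are brought back for week 54, no subject has both scores, so the data cannot estimate the relation between them.

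**Cost.** SAP wording and a little more analysis work, with no new visits. Intervals become about 6-8% wider, and simulated power is about 80-82% against 81-83% for LOCF at the plan's loss split.

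If off-drug visits with a treatment-policy estimand were ever adopted, power would need restating. For 5.1 points at 38/19 I compute 87.6% Welch power with the SDs as stated (the plan states 82.7%; that discrepancy is a separate matter). If 10% or 20% of the drug arm stop and lose all benefit (assumption), the difference becomes 4.59 or 4.08. The drug SD widens to √(6.4² + 0.1 × 0.9 × 5.1²) = 6.58 or √(6.4² + 0.2 × 0.8 × 5.1²) = 6.72, and power is about 79% or 69%.

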In a recent study, it was shown that a cohort of AD patients without systemic insulin resistance, pSer312-IRS-1 was positively associated with MRI atrophy, whereas p-PanY-IRS-1 was negatively associated with it, in a highly characteristic pattern of regions. The significance of this regional pattern lies in its spatial correlation with the normal IRS-1 brain expression. It is speculated that neuronal-enriched plasma EVs containing IRS-1 may be preferentially derived from brain regions with high levels of IRS-1 expression. Therefore, the IRS-1 phosphorylation pattern seen in these EVs may reflect its phosphorylation status in specific brain regions that suffer brain atrophy in early AD in association with higher burden of brain insulin resistance. These findings provide hope that using these biomarkers may also possibly demonstrate target engagement and follow response to treatment in clinical trials that aim to reverse brain insulin resistance (e.g. liraglutide).

In summary, there is mounting evidence that PD pathogenesis is accelerated by brain insulin resistance and that liraglutide can markedly reduce this abnormality, thereby reducing the motor and non-motor symptoms of the disorder.

SPECIFIC OBJECTIVES:

The primary objective of this clinical trial is to test the therapeutic efficacy and safety of liraglutide treatment of patients with idiopathic PD. The secondary objective is to correlate the magnitude of any observed therapeutic efficacy with degree of reduction in peripheral insulin resistance over the course of drug treatment.

RESEARCH DESIGN AND METHODS:

Study Hypotheses: We hypothesize that global disease status (MDS-UPDRS) and especially cognition in PD patients will improve significantly by the end of daily liraglutide treatment for one year compared to those treated only with the placebo (i.e., drug vehicle). We also hypothesize that the improvement seen in each patient will be proportional to the degree of improvement in peripheral as well as neuronal insulin resistance seen in the treatment period.

Endpoints: The primary outcomes are measures of the drug's effects on motor (assessed by MDS-UPDRS III) and non-motor symptoms of PD (assessed by NMSS and MDRS-2) after 52 weeks of treatment at full tolerated dose. The secondary outcomes are measures of the association between liraglutide's effects on peripheral insulin resistance, markers of insulin resistance on plasma EVs enriched for neuronal origin, PD symptoms and safety.

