- The subject has any clinical AE, laboratory abnormality, intercurrent illness, or other medical condition that indicates to the PI that continued participation is not in the best interest of the subject or if it requires the subject to stop taking levodopa or other medications essential to the treatment of Parkinson's disease. Subjects experiencing AEs that are present at the end of their participation in the study should receive follow-up, as appropriate. If possible, the outcome of any AE resulting in withdrawal from the study or that was present at the end of the study will be followed until resolution or return to baseline condition, particularly if the AE was considered by the PI to be related to the study drug;
- The subject requires a concomitant medication that is prohibited in the study;
- The subject wishes to withdraw consent from the study in the absence of a medical need to withdraw, as determined by the Investigator;
- The PI concludes that it is in the best interest of the subject to discontinue study treatment;
- The subject is noncompliant; or
- If pregnancy is suspected while the subject is receiving study treatment, the study medication must immediately be withheld until the result of pregnancy testing is known. If pregnancy is confirmed, the study medication will be permanently discontinued and the subject withdrawn from the study. Reasonable attempts will be made to follow the pregnancy to conclusion in order to obtain information regarding the outcome.

The PI must complete all applicable final visit procedures (e.g., safety laboratory parameters, ECG, physical examination, vital signs [including orthostatic BP and HR]) and study documentation for subjects who withdraw from the study treatment and specify the reason for their withdrawal. Once subjects withdraw from the study, they will revert to the care of their usual physician for treatment/management of their disease as appropriate.

Subject Replacement: A subject who withdraws from the study may not reenter the study.

Rationale for Study Population: (see Background and Significance)

Visit Procedures: (see Study Schedule)

Assessments for Efficacy: The efficacy of liraglutide will be assessed by measures of the drug's effects versus placebo on PD motor and non-motor symptoms quantified on the following scales after study medication titration in active and placebo groups:

- MDS-UPDRS part I, II, III and IV changes from ON medication baseline at 28 and 54 weeks

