- MDS-UPDRS part III changes from OFF medication baseline at 28 and 54 weeks
- Non-Motor Symptoms Scale (NMSS) changes from ON medication baseline at 28 and 54 weeks

- PDQ-39 Quality of Life scale changes from baseline at 28 and 54 weeks
- MDRS-2 changes from ON medication baseline at 28 and 54 weeks. This test assesses overall cognitive functioning on 5 subscales measuring specific abilities including attention, initiation/perseveration, construction, conceptualization, and memory.
- To complement the MDRS-2, additional neuropsychological assessment tools will include:
 - Delis-Kaplan Executive Function System (DKEFS) Verbal Fluency, a standardized assessment tool with robust psychometric properties. Verbal fluency has been established as a highly sensitive cognitive construct to neuropathology in individuals with PD (e.g., sensitive to striatal pathology or dorsolateral frontal dysfunction).
 - Geriatric Depression Scale
 - The Parkinson's Anxiety Scale.
 Inclusion of these brief mood measures will assist in assessing drug effects on the subjects' health-related quality of life.

Assessments for Safety: Safety and tolerability will be assessed by changes in vital signs, weight, clinical laboratory measures, and adverse events. Routine laboratory studies performed at the beginning and the end of the study will include CBC, renal function, liver function, serum amylase, serum lipase, serum calcitonin⁷⁷, and fasting serum glucose and insulin. In addition, an ECG will be performed at baseline and follow-up visits. The number of patients completing the study will be calculated and will establish the tolerability of the study compound at the studied doses. It is expected that over 80% (43 subjects) will safely complete the study.

Other Assessments: Measures of peripheral insulin sensitivity will be used to test the association of changes in such sensitivity to changes in MDS-UPDRS and MDRS-2 scores from baseline to 28 and 54 weeks. Surrogate measures of peripheral insulin sensitivity will be used, specifically the homeostasis model assessment of insulin resistance (HOMA-IR) and the quantitative insulin sensitivity check index (QUICKI).^{61,62} HOMA-IR is defined as fasting glucose (mmol/L) × fasting insulin (mU/L)/22.5. QUICKI is defined as $1/[\log \text{fasting insulin (mU/L)} + \log \text{fasting glucose (mg/dL)}]$.

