Sample Size Calculation: This is a randomized, double-blinded, placebo-controlled clinical trial that aims to evaluate the effects of liraglutide on motor and non-motor symptoms in patients diagnosed with PD. The primary outcome of this study will be the difference in MDRS-2 scores at baseline and follow-up (52 weeks after titration) between the active and placebo control group. The power analysis was performed utilizing data reported in a previous study using a similar GLP-1 agonist (**Table 1**). While score changes associated with active medication were not compared to a placebo group but to a cohort of patients treated with “conventional PD medication”, this data represent the closest approximation available for power analysis and sample size calculation.

With a total of 57 patients (38 in the drug group and 19 in the placebo group), the study will have an 82.7% chance of rejecting the null hypothesis of equal means, assuming an average critical difference of 5.1 points on the MDRS-2 and a standard deviation of 6.4 for the drug group and 5.3 for the placebo group with a significance level (alpha) of 0.050 using a two-sided two-sample unequal-variance t-test.

This sample allows for a 12% dropout of up to 6 subjects (e.g., if they are diagnosed with T2D during the course of the study) and still maintain 81.3% power with a total of 51 patients (i.e., 36 cases in the drug group and 15 cases in the placebo group). If the rate of drop out is higher than anticipated, the study will enroll and randomize additional subjects; subjects will be enrolled/randomized in multiples of 3 subjects in order to maintain the 2:1 randomization. The additional enrolled subjects will aim to maintain the power of the study. In total, up to 63 patients will be enrolled and randomized. No more than 42 patients, including drop outs, will be exposed to the drug during the trial.

Statistical Methods: The analysis populations for this study are defined as:

1. Full Analysis Set (FAS): all randomized subjects who receive at least one dose of study drug and have a baseline and at least one post-baseline efficacy score (MDRS-2 and MDS-UPDRS).
2. Per-Protocol (PP) population: a subset of the FAS population, excluding subjects with major deviations from the protocol that may substantially affect the results of the primary efficacy analysis.
3. Safety population: all randomized subjects who receive at least one dose of study drug.

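### The plan both applies and disclaims a multiplicity adjustment, and names one primary endpoint in one place and three in others, so the same result can be read as positive or negative.

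*Combined protocol and SAP*

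**What the plan says.** **Multiplicity.** Two sentences in the section Inferential Statistics on Primary Efficacy Parameter(s) deal with multiple testing, and each covers both the primary and the secondary endpoints:

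- "Hochberg's method for adjustment for multiple testing separately for the primary end points and secondary endpoints will also be used"
- "No adjustments have been made to the Type I error rate for the multiple comparisons of the primary or secondary endpoints", with the reason that this is a phase II study and the advice to interpret results appropriately.

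**Primary endpoint.** It is defined in three places:

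- Sample Size Calculation, one endpoint: "The primary outcome of this study will be the difference in MDRS-2 scores at baseline and follow-up". Power is computed "with a significance level (alpha) of 0.050 using a two-sided two-sample unequal-variance t-test".
- Endpoints (Research Design and Methods), three endpoints: "effects on motor (assessed by MDS-UPDRS III) and non-motor symptoms of PD (assessed by NMSS and MDRS-2").
- The primary analysis paragraph, three endpoints, with the motor scale named only as UPDRS: "changes in UPDRS, NMSS, and MDRS-2 scores between baseline and Week 54".

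**Medication state.** Assessments for Efficacy lists part III both ways: "MDS-UPDRS part I, II, III and IV changes from ON medication baseline at 28 and 54 weeks" and "MDS-UPDRS part III changes from OFF medication baseline at 28 and 54 weeks". No section says which state gives the primary motor score.

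**Secondary endpoints.** The secondary analysis section lists each PDQ-39 domain and the total, the DKEFS, the Geriatric Depression Scale and the Parkinson's Anxiety Scale, without counting the tests. The Endpoints paragraph describes the secondary outcomes differently, as associations among insulin resistance, vesicle markers and symptoms, plus safety.

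**The concern.** The primary endpoint and the multiplicity rule together decide whether a trial has met its objective. Here both are stated in more than one way, and no sentence says which version governs. No ranking of the three endpoints is given, and no rule on whether one or all must succeed.

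The stated power assumes one endpoint tested at 0.05. That fits a single primary or unadjusted testing, but not Hochberg across three. If the conflict remains when the data are unblinded, the reading could be chosen with the p-values in view. In that case the family-wise error rate is not defined, and the stated power may not describe the test that is reported.

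**Working it through.** **Inputs, all from Sample Size Calculation.** MDRS-2 difference 5.1; SD 6.4 (drug) and 5.3 (placebo); two-sided Welch t-test at 0.05; 38/19 patients, or 36/15 after dropout; up to 63 randomized, which is 42/21 at 2:1. The documents give no correlations between endpoints and no effects for the other two, so those below are assumptions.

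**Step 1: the plan's own power.** SE = √(6.4²/n₁ + 5.3²/n₂), Satterthwaite degrees of freedom, noncentral t with noncentrality 5.1/SE.

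- 36/15: SE = √(1.138 + 1.873) = 1.735, df 31.5, noncentrality 2.94, power 81.3%. This reproduces the stated 81.3%.
- 38/19: SE = √(1.078 + 1.478) = 1.599, df 42.8, noncentrality 3.19, power 87.6%. The plan states 82.7%, which the stated test gives only if the two SDs are exchanged between arms (0.8270). That is a separate correction; 87.6% is used here because it follows from the stated inputs.

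The exact match at 36/15 confirms that the power basis is one endpoint at 0.05.

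**Step 2: Hochberg on three endpoints.** Order the p-values. If the largest is ≤ 0.05, all three are rejected. If not, and the middle one is ≤ 0.025, the two smaller are rejected. If not, the smallest must be ≤ 0.05/3 = 0.0167.

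| Result | MDRS-2 sole primary | Three primaries, unadjusted | Three primaries, Hochberg |
|---|---|---|---|
| MDRS-2 p = 0.03, others > 0.05 | positive | positive | negative (0.03 > 0.0167) |
| NMSS p = 0.02, others > 0.05 | not a primary success | positive | negative (0.02 > 0.0167) |

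For the first row, the critical t times SE gives the observed MDRS-2 differences on which the readings disagree, at the planned SDs:

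- 38/19: 2.017 × 1.599 = 3.22 to 2.492 × 1.599 = 3.98 points.
- 36/15: 2.038 × 1.735 = 3.54 to 2.528 × 1.735 = 4.39 points.

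**Step 3: family-wise error.**

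- One primary: 5%. Hochberg on three: 4.1% to 4.9% in simulation at assumed correlations 0.7 to 0.
- Three unadjusted, independent: 1 − 0.95³ = 14.3%.
- Three unadjusted, assumed equal correlation 0.3, 0.5, 0.8: 13.6%, 12.5%, 9.8%.
- Only if part III were tested both ON and OFF as primaries: 1 − 0.95⁴ = 18.5% if independent, or 16.8% with an assumed ON–OFF correlation of 0.8.

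**Step 4: MDRS-2 power at 0.0167, the worst case under Hochberg.**

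| Patients | α = 0.05 | α = 0.0167 |
|---|---|---|
| 38/19 | 87.6% | 75.4% |
| 36/15 | 81.3% | 66.0% |
| 42/21 (no dropout) | 90.7% | 80.4% |

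The loss shrinks if the other endpoints respond. With assumed effects of 0.5 to 0.8 SD and correlation 0 to 0.3, simulated MDRS-2 power under Hochberg is about 78–84% at 38/19 and 69–76% at 36/15. Under the same assumptions the chance of at least one Hochberg rejection is about 82–97% and 74–93%. With the other two null it is about 76% and 67%.

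**The case against.** The Hochberg sentence says the method will *also* be used and closes a list of further analyses. One could therefore read the plan as unadjusted tests first, with Hochberg-adjusted results alongside. A phase II trial may choose not to adjust, and this plan discloses that choice and asks for cautious interpretation. On that view 14.3% is an accepted rate, and the defect is one of drafting.

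Part of this stands. Unadjusted testing is a legitimate choice here. But the plan never calls Hochberg supplementary, and a flat statement that no adjustments are made contradicts it even on that reading. The conflict between one primary and three remains, and advice to interpret results appropriately is not a decision rule.

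Three narrower points also stand:

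- If success means at least one rejection, MDRS-2 power is not the power of that rule. The figures of 75.4% and 66.0% are conservative, just below the 76% and 67% obtained when the other two endpoints are null.
- The four-test error rates are conditional, because no section proposes both ON and OFF as primaries.
- The two differing descriptions of the secondary outcomes should be settled at the same time, since a Hochberg family needs a fixed membership.

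**Conclusion.** The concern holds and must be fixed before unblinding. The current text supports a single primary at 0.05, three unadjusted primaries, or three primaries under Hochberg, and a result such as MDRS-2 p = 0.03 alone changes from positive to negative between them.

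Family-wise error is 5% or 14.3% depending on the reading; 14.3% assumes independence, and the rate falls to 9.8% at an assumed correlation of 0.8. Worst-case MDRS-2 power under Hochberg is about 12 points below the single-primary figure at 38/19 (87.6 − 75.4 = 12.2) and about 15 points below at 36/15 (81.3 − 66.0 = 15.3). These losses rest on the plan's own difference and SDs and on no help from the other two endpoints. The contradiction itself rests on no assumption.

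**What to change.** Before unblinding:

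1. Keep one of the two multiplicity sentences and delete the other.
2. Use one primary definition in Endpoints, Sample Size Calculation and the primary analysis section, naming the MDS-UPDRS part and the ON or OFF state.
3. State what counts as success.
4. List the secondary family by name, and reconcile the Endpoints paragraph with the secondary analysis section.

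Workable choices:

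- **Option A: MDRS-2 as the single primary at two-sided 0.05.** MDS-UPDRS III and NMSS join the named secondary family under Hochberg, with a statement on whether that family is tested only if MDRS-2 succeeds. This keeps the existing power basis; the cost is that the motor and NMSS outcomes lose primary status.
- **Option B: exactly three primaries under Hochberg, success being at least one rejection.** State worst-case MDRS-2 power as 75.4% (38/19) and 66.0% (36/15), and give power for at least one rejection separately with its assumptions. The cost is a less favourable worst-case figure.
- **Option C: three primaries without adjustment.** Delete the Hochberg sentence and state a family-wise error of up to 14.3%.

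All three need text changes and the submission of an amendment, but no new data, visits or patients. The 82.7% power figure should be corrected separately.
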